8.3.3. Analysis sets

We propose to test efficacy and safety of experimental treatment using the full analysis set. We include in the analysis all patients that accomplished selection criteria and receive one drug exposure.

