8.7. Scientific committee review

A Steering Committee (SC) has been established for this study. Initially, it is composed of the investigators, the study medical scientist, the Scientific Global Coordinator and two physicians expert in radium-223 management.

The SC will meet on demand to review, discuss and evaluate all of the gathered safety data. In case of any arising safety concern, these meetings can also be called at any time at request of a participating investigator. At these meetings, MedSIR and the participating investigators must reach a consensus on safety data. MedSIR will prepare minutes from these meetings and circulate them to each investigator for comment prior to finalization.

The study site Investigators and MedSIR will review patient data at least every four months. Each study site Investigator will monitor patients data for serious toxicities on an ongoing basis.

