## **6. Analysis sets**

### Full analysis set

All patients that accomplish selection criteria and receive at least one dose of study medication.

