### Per protocol set (PP)

All patients that accomplished selection criteria, received the study drug according to protocol timelines and dosing, and had no major protocol deviations. Criteria for determining the PP group assignment would be established by the Steering Committee before the statistical analysis begins. Patients without AR-V7 status in the study will be excluded.

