### **6.1 Protocol Deviations**

Protocol deviations will be recorded in the EXPERIOR database. A by-patient listing of protocol deviations and a by-patient listing of inclusion and exclusion criteria not met will be provided.

Major protocol deviations are defined as those deviations from the protocol likely to have an impact on the perceived efficacy and/or safety of study treatment.

To determine the per protocol set, all protocol deviations will be reviewed prior to database lock to determine which ones should be classified as major deviations. Patients with major protocol deviations will be excluded from the per protocol set.

Major protocol deviations may be discussed in the data review meeting. Criteria for determining full analysis set would be established by the Steering Committee (SC) before the statistical analysis begins.

Major protocol deviations and any action to be taken regarding the exclusion of subjects or affected data from specific analyses are defined below.

A summary of the number and percentage of subjects with a major protocol deviation by type of deviation will be provided. Also, a by-subject listing of major and minor protocol deviations will be provided.

Description	Category	Grade*	Rationale	Comments
Adult < 18 years	Inclusion/Exclusion criteria	Major	Safety	Automatic check
Informed consent form not signed	Inclusion/Exclusion criteria	Major	GCP breach	Automatic check. Patient data could not be used for efficacy assessment
Patient has not histologically confirmed adenocarcinoma of the prostate without neuroendocrine differentiation or small cell features	Inclusion/Exclusion criteria	Major	Efficacy	Manual Review
Patient has not bone metastases due to the prostate cancer and presence of visceral metastases	Inclusion/Exclusion criteria	Major	Efficacy	Manual Review
Serum testosterone of > 1.7 nmol/L (or > 50 ng/dL) at screening	Inclusion/Exclusion criteria	Major	Efficacy Safety	Automatic check
<24 weeks of treatment with abiraterone acetate or enzalutamide within its approved label indication and discontinuation <4 weeks prior to start of study drug at day 1	Inclusion/Exclusion criteria	Major	Efficacy Safety	Manual Review

EudraCT number: 2016-001888-36

Castration-naïve patients treated >six cycles with docetaxel	Inclusion/Exclusion criteria	Major	Efficacy	Manual Review

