No baseline tumor assessment	Inclusion and Exclusion criteria/ Study procedure	Major	Efficacy	If not baseline values any post-baseline data indicating presence of new bone lesions/visceral lesions could be evaluated as evidence of PD Flag if baseline data (CT and bone scans) are >28 days before day 1 cycle 1.

No post-baseline data indicating presence of ≥ 2 new bone lesions or progression as per RECIST 1.1	Study procedure	Major	Efficacy	No evidence of Radiological PD for patients not discontinued due to increased PSA, symptoms or clinical deterioration.
Visits out of window	Study procedure	Minor	Safety	If not performed every 28 days +7 days until EOT; if not performed every 3 months after EOT or if EOS not performed within 3 months after progression, lost to FUP.
Local laboratory tests out of window	Study procedure	Major	Safety	If tests scheduled for day 1 of all cycles (including screening) not performed within 72 hours prior to the dose
Screening assessments out of window	Study procedure	Case by case	Safety	If done >28 days before day 1 cycle 1. Not applicable to local lab tests.
Assessments not done during treatment period (lab value, HRQoL..)	Study procedure	Case by case	Safety	Not applicable to Radiological Assessments. Flag if systematically not done.
Blood sample for translational study not obtained or obtained at incorrect timepoint	Study procedure	Case by case	Efficacy	Depending on which sample is not collected.
Blood sample for translational study obtained out of window at screening	Study procedure	Case by case	Efficacy	Sample not obtained within 72 hours prior to the first dose
Adequate follow-up	Study procedure	Major	Efficacy	If no post-treatment evaluation according to protocol
Prohibited medication was taken	Concomitant medication	Major	Efficacy	If any therapies intended for the treatment of cancer prior to EoT (Cytotoxic chemotherapy, other systemic radioisotopes,

EudraCT number: 2016-001888-36

				radiotherapy, abiraterone acetate, enzalutamide or any antiandrogen)
Prohibited medication was taken	Concomitant medication	On a case by case	Efficacy Safety	If another investigational drug prior to EoT
Subject not withdrawn as per protocol	Administrative and Other	Major	GCP	If data is obtained after withdrawal

\* Major protocol deviation excludes from the full analysis set

\*\* Identification of clinically relevant conditions from the Medical History

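### The SAP gives incompatible rules for the primary analysis set: the full analysis set definition keeps patients with on-study deviations, while a footnote in section 6.1 removes them

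*SAP*

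**What the plan says.** **The definition.** SAP section 6 defines the FAS as "All patients that accomplish selection criteria and receive at least one dose of study medication". Protocol 8.3.3 agrees: "We include in the analysis all patients that accomplished selection criteria and receive one drug exposure". SAP 8.4.1 repeats the same two conditions. SAP 7.1.1 makes the FAS the primary set and the per protocol set supportive.

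**Deviations.** The body of SAP 6.1 ties major deviations to the other set: "Patients with major protocol deviations will be excluded from the per protocol set". The footnote to the table in the same section says "Major protocol deviation excludes from the full analysis set".

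**Who decides.** SAP 6.1 also says "Criteria for determining full analysis set would be established by the Steering Committee (SC) before the statistical analysis begins". For the per protocol set, section 6 has a nearly identical sentence: "Criteria for determining the PP group assignment would be established by the Steering Committee before the statistical analysis begins". Protocol 8.7 describes the committee: "it is composed of the investigators, the study medical scientist, the Scientific Global Coordinator and two physicians expert in radium-223 management".

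**How patients are analysed.** Under SAP 7.1.1, 8.5 and Appendix I Table 1, patients with no post-baseline scan are censored one day after first treatment, patients without progression are censored at their last evaluation, and death before the first assessment is an event.

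**The concern.** Two analysts working from this SAP could run the primary test on different patients. One would use the section 6 definition. The other would follow the footnote and remove anyone with a deviation graded Major. Several of those grades rest on things that happen after dosing: no scan or a first scan before 8 weeks, overdose or underdose, laboratory tests outside the 72-hour window, or radiotherapy before the end of treatment. Selecting on such facts biases the PFS estimate, and a single-arm test against a fixed 3 months has no comparator to absorb the bias. The FAS would also nearly merge with the per protocol set, so the supportive analysis would lose its purpose.

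The setting makes a clear definition more important. The trial is open-label, sites assess progression without central review (SAP 7.1), the committee includes investigators, and an interim analysis has already been run for a congress abstract (SAP 7.6).

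**Working it through.** **1. The plan's own figure.** Inputs from Protocol 8.2: null median 3 months, target 6.3 months, one-sided alpha 0.05, power 80%, accrual 23 months plus 11 months of follow-up, 25% AR-V7-positive.
- Events needed: ((1.645 + 0.842) / ln(6.3/3))² = (2.487/0.742)² = 11.23.
- With hazard h = ln2/6.3 = 0.110 per month, P(event) = 1 - (e^(-11h) - e^(-34h))/(23h) = 1 - (0.298 - 0.024)/2.530 = 0.892.
- n = 11.23/0.892 = 12.6, rounded up to 13 AR-V7-positive patients; 13/0.25 = 52. The planned total reproduces.
- Power with n patients is Φ(0.742·√(0.892n) - 1.645): 81.1% at 13, 78.3% at 12, 75.1% at 11. Losing one or two patients from the cohort that drove the sample size takes it below 80%.

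**2. The texts side by side.**

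| Patient | Under the footnote (SAP 6.1 grade Major) | Under the other SAP text |
|---|---|---|
| Dies before any scan | Removed | Event at death (Appendix I Table 1) |
| Alive, no post-baseline scan | Removed | Censored one day after first treatment (8.5) |
| Radiotherapy to bone before end of treatment | Removed | PFS event (7.1.1) |
| Overdose, underdose or late laboratory test | Removed | Kept by the FAS definition; no censoring rule names them |
| No radiological progression on record | Possibly removed; the row's scope is unclear | Censored at last evaluation (7.1.1, Appendix I Table 1) |

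**3. Size under assumed rates.** The setup was 200,000 simulated trials per case with n = 52, exponential PFS in continuous time (scan schedule ignored), uniform accrual over 23 months and cutoff at month 34. With d events and total time T, E = T·ln2/3, and the test rejects if (E - d)/√E > 1.645. The exponential maximum-likelihood test named in SAP 7.1.1 agrees within 0.3 percentage points.
- *Early events removed, true median 3 months.* Removing 0, 1, 2 or 4 events that fall before day 56 gives type I error of 4.0, 5.1, 6.4 or 9.7%. Counts of 1 or 2 are the more plausible, because Protocol 5.2 puts the first scan at the end of cycle three.
- *Every patient without progression removed, true median 6.3 months, no dropout.* On average 52 × (1 - 0.892) = 5.6 patients go. The estimated median falls to 4.8 months and power to 95%, against over 99.9% with nobody removed.
- *Late-laboratory row, read as any one late test, true median 6.3 months.* At 2, 5 or 10% late tests per dose, a patient with six doses is excluded with probability 1 - (1 - q)^6 = 11, 26 or 47%. About 5, 11 or 20 patients go, the estimated median is 6.1, 5.9 or 5.4 months, and power is 0.998, 0.989 or 0.920. At a true median of 3 months, type I error falls to 2.6, 1.3 or 0.4%.

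The first exclusion biases PFS upward and the other two downward.

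**The case against.** The strongest reply is that this is a slip. The FAS is defined three times (Protocol 8.3.3, SAP 6, SAP 8.4.1) with no exclusion for deviations. SAP 6.1 says deviations are reviewed before database lock in order to settle the per protocol set, and the committee sentence echoes the one for that set. The effect is also small at plausible inputs: type I error of 5-6% against a nominal 5%, and power well above 80% in the total sample. A living, progression-free patient with no scan contributes one day of follow-up, so removing him changes almost nothing.

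Most of this stands, and it limits the weight of the numbers. It does not settle the text, because two separate statements in 6.1 point at the FAS and the SAP does not say which text prevails.

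Three stronger readings are tempting, but the documents do not support them.
- *A reader might infer that the primary set is still open after results were seen.* A definition exists, and 6.1 requires criteria before the analysis begins. SAP 7.6 does not say what the abstract's interim analysis contained or who saw it. Committee membership and the lack of central review are context; they are not evidence that the set will be altered.
- *A reader might infer a severe loss of power.* Removing everyone without progression gives power of 0.86, 0.67 or 0.39 only if 10, 20 or 30% dropout is also assumed. The row's comment limits it to patients not discontinued for rising PSA, symptoms or deterioration, and the row may be only a documentation check.
- *A reader might infer that the case-by-case grades on eligibility rows (creatinine, bilirubin, prior cancer and others) contradict the FAS definition.* They do so only if the footnote governs the FAS. If the table grades deviations for the per protocol set, there is no conflict.

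**Conclusion.** The SAP is wrong as written and must be corrected before the final analysis. The reason is the contradiction over who enters the primary test; it does not depend on the simulated figures. Those rest on assumed deviation rates and exponential PFS. The plausible early-event case moves type I error by one or two percentage points (about 6 points if four events are removed). The fall to about 4.8 months is an upper bound under an unclear row. No single direction of bias can be claimed.

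A separate, lesser item: SAP section 6 assigns safety analyses to the safety set (everyone dosed), but the tables in SAP 8.4 use the FAS, as Protocol 8.3.3 does: "We propose to test efficacy and safety of experimental treatment using the full analysis set". This leaves treated but ineligible patients out of the safety tables. If the footnote were followed, it would also leave out treated patients with a major deviation such as an overdose.

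**What to change.** 1. Change the footnote in SAP 6.1 so that a major deviation excludes from the per protocol set.
2. Delete the 6.1 sentence on Steering Committee criteria for the FAS, or redirect it to the per protocol set.
3. Keep the section 6 definition as the only FAS definition, and state that selection criteria are judged on status at enrolment. Some criteria in Protocol 4.2 run on during the study (LHRH therapy, contraception, no other interventional study). Later breaches of these should affect only the per protocol set, as should post-baseline events, missing assessments, and dosing or procedural deviations. Without the enrolment rule, a promise that nothing post-baseline removes a patient would collide with the requirement to meet the criteria.
4. State that the case-by-case grades in the eligibility rows of 6.1 govern the per protocol set only.
5. Use the safety set throughout SAP 8.4, and either align Protocol 8.3.3 or record the departure from it.

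The cost is SAP wording plus a note on, or alignment of, Protocol 8.3.3. No new data are needed and the planned 52 patients are unchanged.

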## 7. Statistical strategy

Below are detailed the statistical aspects of the data analysis.

### 7.1 *Efficacy analysis*

All efficacy analyses will be based on the full analysis set. The primary analysis will be also assessed in per protocol set. Tumor response, bone lesion, SSE evaluation, biochemistry determinations, and predictive biomarkers are obtained at investigators' sites. There is not central and independent review of evaluations. Methodology for tumor assessment will be according to the RECIST version 1.1 and the PCWG2 criteria.

#### 7.1.1 *Primary analysis*

The primary efficacy endpoint is the median PFS achieved with radium-223 treatment. The PFS will be evaluated at the first 34 months period of the study. The PFS will not be evaluated at the 2-years extension of the study for safety.

PFS is a composite endpoint defined as the time from the start of the radium-223 treatment to disease progression in bone or soft-tissue, symptoms, or death, according to the modified PCWG2 criteria.

Objective radiographic disease progression is defined as the presence of at least one of the following conditions:

- Bone lesion progression (appearance of  $\geq$  two new bone lesions compared to baseline).
- Soft-tissue lesion progression according to the RECIST criteria version 1.1.
- Presence of symptomatic skeletal events (pathological fractures, spinal cord compression, radiation or surgery to bone), which should have been reported as adverse event/serious adverse events.

Patients with no progression will be censored at the date of their last evaluation (see Table 1 – Appendix I).

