3.2. Study schedule

The design of this study is divided into three well-defined phases:

- **Screening phase**

During this phase, subject eligibility is determined, including the documentation of baseline characteristics. This phase of the study will begin once the informed consent is signed by the patient and the procedures to be performed are described in section 5.1 of the protocol.

- **Treatment phase:**

When a patient is identified and all the study screening criteria have been met, a baseline blood sample will be collected to perform CTCs the patient will be treated with radium-223 at a dose of 55 kBq (after 2015 NIST implementation) per kilogram body weight, given at four-week intervals for six intravenous (IV) injections.

Patients will receive study treatment according to the protocol and will be prematurely discontinued if one of the following situations arises:

- Disease progression is confirmed radiologically and unequivocally. An event for progression will be determined by The Prostate Cancer Clinical Trials Working Group (PCWG2) modified criteria defined as the time from inclusion to the first event in clinical, radiological, or biochemical progression, or death as[21]:

- Bone metastases: The appearance of \geq two new lesions, and, for the first reassessment only, a confirmatory scan performed six or more weeks later that shows a minimum of two or more additional new lesions. The date of progression is the date of the first scan showing the changes.

- Soft-tissue lesions: Assesed according to the Response Evaluation Criteria in Solid Tumors (RECIST criteria) version 1.1.[22].

- Symptoms: Consider independently of other outcome measures. Document pain/analgesia at entry and measure repeatedly at three- to four-week intervals. Ignore early changes (\leq 12 weeks) in pain or health-related quality of life (HRQOL) in the absence of compelling evidence of disease progression. Confirm progression of pain or HRQOL endpoints \geq three weeks later.

- Clinical deterioration: Consider independently of other outcome measures. A deteriorating patient is one who moves from one clinical state to a worse clinical state which increases their individual risk of morbidity, including organ dysfunction, protracted hospital stay, disability, or death.[23].

- AEs which, according to the protocol or in the opinion of the investigator, can cause serious or permanent damage or which rule out further treatment with the study drug.

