5.2. Treatment phase: Assessments

All screening assessments must be completed and reviewed to confirm that patients meet all eligibility criteria before treatment starts (day 1). The investigator will maintain a screening log to record details of all patients screened and to confirm eligibility or record reasons for screening failure, as applicable.

Visits are organized in programmed cycles of 28 days (if there are no delays in treatment owing to the occurrence of a side effect). Adjustment of dose level is not permitted. Dose delays are permitted, as described in section 6.11. All visits must occur within \pm 7 working days from the scheduled date, unless otherwise noted in the schedule of assessments. All assessments will be performed on the day of the specific visit unless a time window is specified. Assessments scheduled on the day of study treatment administration should be performed prior to study treatment administration unless otherwise indicated. If a mandatory procedure described in the protocol falls on a bank holiday and/or weekend, this procedure should be performed on the day before or after the holiday (i.e. within a period of \pm 3 working days).

Local laboratory tests scheduled for day 1(before treatment) of all cycles must be performed within 72 hours prior to confirm to the patient if treatment can be followed up. The results of local blood tests should be reviewed, and this review recorded before administration of the study treatment.

Specific study assessments during treatment phase:

During basic safety visits: Day 1of each cycle (every four weeks):

- Assessment of symptoms.
- Physical examination and measurement of weight, vital signs, and ECOG performance status.
- Basic blood test that includes blood count, coagulation, chemistry with renal function analysis (serum creatinine, creatinine clearance according to the Cockcroft-Gault formula), liver function (AST, ALT, AF, GGT, total and direct bilirubin), glucose, sodium, potassium, calcium, chloride, magnesium, uric acid, total protein, albumin, and lactate dehydrogenase.
- PSA determination.
- HRQoL questionnaire (FACT-P, Version 04).
- Assessment of concomitant medications.
- Assessment of AEs.
- Survival.

During full visits: Day 1 of each cycle every three cycles (every 12 weeks):

- Assessment of symptoms.
- Physical examination and measurement of weight, vital signs, and ECOG performance status.

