Appendix 1: Schedule of study assessments and procedures

Study Period	Screening	Treatment period		Follow-up period		
Day	-28 to -1	Each cycle* (every 28 days)	End of treatment **	Every 3 months (Efficacy FUP) ¹²	At time of DP**	EoS (Safety FUP) ¹³
Informed Consent ¹	X					
Baseline signs/symptoms	X	X	X	X	X	
Check of inclusion/exclusion criteria	X					
Brief pain inventory (short form) (BPI-SF)	X					
Medical History ²	X					X
Physical Examination and ECOG status ^{3,4}	X	X	X	X	X	

Study Period	Screening	Treatment period		Follow-up period				
Day	-28 to -1	Each cycle* (every 28 days)	End of treatment **	Every 3 months (Efficacy FUP)¹²	At time of DP**	EoS (Safety FUP)¹³		
Concomitant Medication Reporting ⁵	X	X	X	X	X			
Health-related quality of life (HRQoL) questionnaire ⁶	X	X	X	X	X			
AE reporting ⁷	X	X	X	X	X	X		
Radiological Tumor Assessments ⁸	X	every 3 cycles	X	X	X			
Standard Laboratory Procedures								
Hematology ^{9,^}	X	X	X	X	X			
Biochemistry ^{10, ^}	X	X	X	X	X			
PSA determination [^]	X	X	X	X	X			

Study Period	Screening	Treatment period		Follow-up period			
Day	-28 to -1	Each cycle* (every 28 days)	End of treatment **	Every 3 months (Efficacy FUP) ¹²	At time of DP**	EoS (Safety FUP) ¹³	
Testosterone determination [^]	X						
Treatment Administration							
Radium-223 at dose of 55 kBq/Kg one IV injection		D1 (for a total of six IV injections)					
Research Central Laboratory Procedures							
Blood sample collection (split variant AR-V7 determination) ¹¹	X		X		X		
Blood sample collection (CTC count) ¹¹	X		X		X		

-
- * All visits must occur within \pm 7 working days from the scheduled date.
 - ** If disease progression coincides with the end of treatment visit, the evaluations planned for both visits will coincide, they will only be performed once (including blood sample for central laboratory).

 - ^ Local laboratory tests scheduled for day 1 of all cycles must be performed within 72 hours prior to confirm to the patient if treatment can be followed up.
 - 1. Signed written informed consent obtained prior to any trial-specific procedure.
 - 2. Complete medical history and demographics (including age, gender, and ethnic origin) and all medications taken the last 28 days prior to enrollment will be collected.
 - 3. Physical examination and vital signs (including respiratory rate, blood pressure measurements, heart rate, and body temperature) and weight measurement will be performed prior to enrollment.

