#### **Primary endpoint:**

To determine the efficacy of radium-223 in terms of radiological PFS (rPFS).

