**Appendix I**

Table 1. Censoring rules for PFS

Situation	Date of progression or censoring	Outcome
Progression documented between scheduled visits	
Earliest of:
 

• Date of radiological assessment showing new lesion (if progression is based on new lesion); or

• Date of last radiological assessment of measured lesions (if progression is based on increase in sum of measured lesions); or

• Bone lesion progression (appearance of <math>\geq</math> two new bone lesions compared to baseline); or

• Presence of symptomatic skeletal events (pathological fractures, spinal cord compression, radiation or surgery to bone)

	Progressed
Death before first progression disease assessment	Date of death	Progressed
Death between adequate assessment visits	Date of death	Progressed
No progression	Date of last radiological assessment of measured lesions	Censored
Treatment discontinuation for undocumented progression	Date of last radiological assessment of measured lesions	Censored
Treatment discontinuation for toxicity or other reason	Date of last radiological assessment of measured lesions	Censored
Death or progression after more than one missed visit	Date of last radiological assessment of measured lesions	Censored

EudraCT number: 2016-001888-36

Table 2. Censoring rules for OS

Situation	End date	Status
Death during study follow-up	Date of death	Death
The patient is alive at last follow-up	Date of last follow-up	Censored

EudraCT number: 2016-001888-36

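### The primary PFS definition counts symptoms as an event but the censoring table has no event row for them, so a symptom-only progression can be censored in the trial's favour

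*SAP*

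**What the plan says.** - **Definition.** SAP 7.1.1 and protocol 8.3.1 both run PFS from the start of radium-223 to "disease progression in bone or soft-tissue, symptoms, or death", under modified PCWG2 criteria.
- **Condition list.** The list that follows has three items: at least two new bone lesions, RECIST soft-tissue progression, and symptomatic skeletal events (fracture, cord compression, radiation or surgery to bone).
- **Censoring tables.** In protocol Table 2 and SAP Appendix I Table 1, the rows with outcome Progressed cover those items and death. The row "Treatment discontinuation for undocumented progression" is censored at the last radiological assessment.
- **Endpoint name.** Protocol 2.1 and SAP 5.1 call the primary endpoint radiological PFS. Protocol 3.2 gives a further version, a first event of clinical, radiological or biochemical progression, or death.
- **Symptom data.** For symptoms, protocol 3.2 says "Document pain/analgesia at entry and measure repeatedly at three- to four-week intervals" and "Confirm progression of pain or HRQOL endpoints" at least three weeks later. Section 5.2 and Appendix 1 schedule symptom assessment, concomitant medication and FACT-P every cycle. BPI-SF, which defines asymptomatic at entry, is marked at screening only.
- **Stopping without radiological progression.** The deviation table in SAP 6.1 refers to patients who discontinued for rising PSA, symptoms or clinical deterioration and have no radiological progression.

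**The concern.** The same patient can be coded two ways. By the definition sentence, a patient who stops for worsening symptoms between scans has a PFS event. By the table, if no scan qualifies, he can be censored at the previous scan. Two analysts following the SAP could reach different event counts.

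The direction matters because the comparison is with a fixed number. There is no control arm in which the same handling would apply, and SAP 7.1 states that there is no central review. Every composite event moved to censored lowers the estimated hazard and lengthens the estimated median, which makes it easier to reject PFS of 3 months or less. Patients enter nearly pain-free and are scanned every 12 weeks, so symptoms coming first is plausible, and the SAP's own deviation table anticipates it.

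**Working it through.** **1. The plan's own figure.** Inputs from protocol 8.2: medians 3 and 6.3 months, one-sided alpha 0.05, power 80%, accrual 23 months, further follow-up 11 months, 25% AR-V7-positive.

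- Events = (1.645 + 0.842)² / [ln(3/6.3)]² = 11.23.
- Event probability at 6.3 months, with λ = ln2/6.3: 1 − (e^(−11λ) − e^(−34λ)) / (23λ) = 0.892.
- n = 11.23 / 0.892 = 12.6, so 13; 13 / 0.25 = 52.

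The stated 52 reproduces, so sample size is not at issue. With about 51 events among 52 patients, the test rejects once the estimated median exceeds 3 × exp(1.645/√51) = 3.78 months.

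**2. The passages side by side, for a patient who stops for symptoms with no qualifying scan.**

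| Place | Status |
|---|---|
| Definition sentence | Event |
| Three-item condition list | No event, unless a skeletal event |
| Censoring table | Can be censored at last scan |
| Endpoint name (rPFS) | No event |

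The per-cycle symptom, medication and FACT-P records do not settle it. Protocol 3.2 gives a measurement interval and a confirmation interval, but no scale or cut-off, and nothing in the analysis sections turns these records into a dated event.

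**3. Size.** The documents give no share of first progressions that are symptom-only, so q is assumed. Simulation: N = 52, exponential composite PFS, uniform accrual over 23 months, cut-off at 34 months, scans every 12 weeks (84/30.4375 = 2.76 months). A random share q of events is censored at the last scan, or at day 1 if there is none (SAP 8.5). The test is the SAP's exponential maximum-likelihood test, one-sided 0.05, against 3 months. The one-sample log-rank test gives practically the same rates.

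True composite median 3 months:

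| q | Mean estimated median | False-positive rate | Rate if exit scan documents half |
|---|---|---|---|
| 0% | 3.0 | 4% | 4% |
| 5% | 3.1 | 7% | 5% |
| 10% | 3.25 | 12% | 7% |
| 15% | 3.4 | 18% | 9% |
| 25% | 3.7 | 36% | 14% |

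**4. Hand check of the medians**, ignoring the cut-off. The hazard is ln2/3 = 0.231, so mean time to event is 4.33 months. Let r = exp(−0.231 × 2.76) = 0.5285. Mean time to the last scan is 2.76 × r/(1 − r) = 3.09, or 3.11 with the day-1 rule. A censored patient keeps 3.11/4.33 = 0.718 of his time, so the estimated median is about 3 × (1 − 0.282q)/(1 − q). This gives 3.11, 3.24, 3.38 and 3.72 for q = 5%, 10%, 15% and 25%, in line with the table.

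**5. At the target.** With a true composite median of 6.3 months the test rejects almost always in any case. Only the reported median moves, to about 6.9 months at q = 10% and 7.7 at q = 20%.

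**The case against.** **Symptoms may be loose wording for skeletal events.** The sentence lists bone, soft tissue, symptoms; the bullets list bone, soft tissue, symptomatic skeletal events. Read in parallel, definition and table agree. This is a fair reading, but protocol 3.2 has its own symptom criterion based on pain and HRQoL, so the text does not settle it.

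**If the estimand is rPFS, nothing is miscounted.** The false-positive rates above score a table-based analysis against a symptom-inclusive composite. If the primary endpoint is declared to be rPFS, the table is the right rule and the primary result does not change. That stands, and it is why deleting the word is a clarification and not a correction of bias.

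**Several provisions limit the effect.** Protocol 5.3 schedules CT or MRI and a bone scan within 28 days of progression or end of treatment. The synopsis strongly recommends extra scans when clinical progression is suspected. Scans continue when treatment stops for a reason other than progression. Radiation to bone and most deaths are events. These reduce the bias without removing it: bone progression needs persistence on a scan at least six weeks later, and a patient recorded as stopping for symptomatic progression may fall outside the continued-scan rule.

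**Stronger readings that the documents do not support.** A reader might infer that symptoms cannot be measured at all because BPI-SF is given only at screening. But protocol 3.2 asks for pain and analgesia without naming BPI-SF, and symptoms and medication are reviewed every cycle; what is missing is a rule, not data. A reader might also infer that the sickest patients will be censored systematically. The table allows this but does not establish it, and the simulation recodes a random share, so it shows the effect of losing events and not of informative censoring. Censoring on the stopping date would give larger rates (16% at q = 10%), but the table specifies the last scan.

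**Conclusion.** The concern holds as an inconsistency between the primary event definition and its own censoring rule, with a bias that can only favour a positive result. Its size cannot be taken from the documents. Under the table's last-scan rule, a 10% symptom-only share would raise one-sided error against a 3-month composite median from about 4% to about 12%, or about 7% if the exit scan catches half. The figures rest on exponential PFS, an assumed and random share, and a composite estimand. They illustrate sensitivity and do not predict this trial's error rate. This should be fixed before the primary analysis; it does not invalidate the design or the sample size.

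**What to change.** Reconcile protocol 3.2, 8.3.1 and Table 2 with SAP 5.1, 7.1.1 and Appendix I Table 1, so that the definition and both censoring tables name the same events. Either route works:

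- **Radiological endpoint.** Delete symptoms from the definition sentence, or replace it with symptomatic skeletal events, and state that the primary endpoint is rPFS. Note that this alone leaves the primary result unchanged.
- **Composite endpoint.** Keep symptoms, state the instrument, threshold and confirmation that make an event, and add a dated Progressed row to both tables.

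In either case, pre-specify one sensitivity analysis in which treatment discontinuation for symptomatic, clinical or otherwise undocumented progression is an event on the discontinuation date. Report its median and its test against 3 months beside the primary result.

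The first route and the sensitivity analysis use data already collected and cost wording plus one extra run; the second may need an additional questionnaire at existing visits. The sensitivity median will probably be somewhat less favourable.
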